2. Study Objectives: The objective of this study is to investigate the neural mechanisms of gait adaptation and the effects of transcutaneous electrical nerve stimulation (TENS) on adaptability during split-belt treadmill training in PwMS. Functional near-infrared spectroscopy (fNIRS) will be used during a split-belt treadmill training paradigm to assess cortical activation during gait adaptation. Additionally, the effect of split-belt treadmill training coupled with TENS on gait adaptability in PwMS will be tested with active and inactive TENS during split-belt treadmill sessions. Cortical activation and the effect of TENS on gait adaptability will be compared between neurotypical adults and PwMS to assess differences that can be attributed to multiple sclerosis. Specifically, we hypothesize that the sensorimotor integration areas of the cortex including the supplementary motor areas (SMA), premotor cortex (PMC), somatosensory cortex (S1), and posterior parietal cortex (PPC) will have heightened activity during split-belt treadmill training, compared to when the belts are moving the same speed. Additionally, we hypothesize that the application of TENS during split-belt treadmill training will significantly increase gait symmetry improvements when compared to split-belt treadmill training alone and will also result in improved adaptation retention.

B. Background and Significance

1. Study Significance: Studies have consistently demonstrated that split-belt treadmill training can acutely improve gait symmetry, however there is minimal application of this paradigm toward enhancing or prolonging these improvements. The impact of this study is not only revealing the cortical mechanisms of sensorimotor adaptation and improving gait symmetry, but a necessary step towards translating these improvements out of the lab into a real-world environment thereby persistently improving mobility for not only PwMS but the tens of millions of individuals who experience gait dysfunction.

INSTITUTIONAL REVIEW BOARD NON-EXEMPT PROTOCOL TEMPLATE

2. Our recent studies showed robust gait symmetry improvements in PwMS following split-belt treadmill training and additionally has demonstrated that TENS improves positional awareness and motor learning during a stepping task. The combination of these findings leads us to want to investigate the neural mechanisms of split-belt treadmill training and if TENS can enhance to effects of split-belt treadmill training.

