A. Study Type and Design: This is a crossover study with both PwMS and age and sex-matched neurotypical controls. 30 PwMS and 20 neurotypical controls be randomized into two groups and will participate in two split-belt treadmill training sessions while outfitted with cortical fNIRS and TENS devices on their bilateral tibialis anterior and rectus femoris. The first group will complete split-belt treadmill training with TENS OFF during the first visit and TENS ON during the second visit. The second group will complete split-belt treadmill training with TENS ON during the first visit and TENS OFF during the second visit to control for a learning effect. In between visits there will be a 4-week washout period. Participants will receive TENS only during the 10-minute split-belt adaptation period of the paradigm. During all other periods the TENS will be OFF.

B. Sample size, statistical methods, and power calculation

1. Total number of subjects who will be approached (including screen fails, controls and subject withdrawals) to reach enrollment numbers for the lifetime of the study for this investigator's site: 60
2. Total number of subjects to be enrolled at this site: 50

INSTITUTIONAL REVIEW BOARD NON-EXEMPT PROTOCOL TEMPLATE

3. Brief Description/justification for the proposed sample size in *lay terms*: From our preliminary data we computed a large effect size of 1.01 for change in brain activity in the SMA from baseline walking to split-belt treadmill training. According to our power analysis, to maintain an alpha of 0.05 and a power of 0.8, at least 10 participants per group are needed to detect significant changes in brain activity.
4. Simple randomization will occur (TENS first or TENS second) for both groups (PwMS and neurotypical controls).
5. No masking will occur in this study.

C. Subject Criteria (See Vulnerable Populations appendix 1, if applicable): PwMS and neurotypical controls from ages 18-86. All races and genders are included.

1. Inclusion criteria:

- A diagnosis of relapsing remitting multiple sclerosis OR a neurotypical adult (ages 18-86)
- Not experiencing an active relapse
- Able to stand and walk without an assistive device
- Able to walk for three tenths of a mile without stopping to rest
- MS participants must have a neurologist confirmed diagnosis of relapsing-remitting MS.
- MS participants must be independently ambulatory in the community, expanded disability status scale (EDSS) score < 5 (clinical measure of MS severity).

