- 3 Trained graduate students and the principal investigator will determine whether the subject is able to give consent. People with cognitive impairments and minors will be excluded from this study due failing to meet the inclusion/exclusion criteria.

D. Specific procedures and techniques used throughout the study

1. Laboratory tests
 - **Gait Adaptation.** This will be assessed using inertial sensors and 3-D motion capture. Both use noninvasive markers that are placed on the lower limbs of the participants. Our outcome measures assessing gait adaptation will be step length asymmetry (SLA). Step length is quantified by the anterior-posterior distance between heel markers at leading limb heel strike. Step length asymmetry will be calculated by subtracting the step length of the less affected limb from the step length of the more affected limb for each consecutive step and normalized to participant stride lengths and will be assessed continuously throughout each gait trial. We will use step length asymmetry to identify 1) the adaptation rate during the split-belt adaptation period to assess speed of adaptation between conditions and groups, and 2) adaptation savings, or the difference in adaptation rate between visit 2 and visit 1, to quantify adaptation retention between conditions and groups.

INSTITUTIONAL REVIEW BOARD NON-EXEMPT PROTOCOL TEMPLATE

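### The hypothesis that TENS increases gait symmetry gains is tested at best indirectly, through adaptation rate, and savings is not a separate test of TENS on retention

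*Combined protocol and SAP*

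**What the plan says.** Section I.A.2 states two TENS hypotheses. The first is that "the application of TENS during split-belt treadmill training will significantly increase gait symmetry improvements when compared to split-belt treadmill training alone"; the second is that retention of the adaptation will be better. Section I.B.2 uses the same idea of symmetry improvement for the group's earlier work: "Our recent studies showed robust gait symmetry improvements in PwMS following split-belt treadmill training".

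Section III.D.1 takes SLA as the gait measure. It is formed by "subtracting the step length of the less affected limb from the step length of the more affected limb", scaled to stride length, and it "will be assessed continuously throughout each gait trial". Two quantities are derived from it. Adaptation rate is taken in the split-belt period, is described as speed, and has no formula. Savings is the difference in that rate between visit 2 and visit 1, and is meant to capture retention.

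Section III.D.2 adds ten minutes of tied-belt deadaptation at preferred speed, so that symmetry changes can be followed between groups.

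Section II.A sets out the crossover: "The first group will complete split-belt treadmill training with TENS OFF during the first visit and TENS ON during the second visit"; the second group has the reverse order. TENS runs only in the split-belt period: "During all other periods the TENS will be OFF". Section II.B.5 says "No masking will occur in this study".

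The SAP (V.C) fits mixed models with group, visit, TENS condition and their interactions. It names rate and savings as the adaptation outcomes; the only other modelled outcome is the fNIRS measure, HbO beta.

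**The concern.** The first hypothesis is about how much symmetry is gained. The outcomes are a speed and a difference of speeds. A participant can reach the same plateau faster, or reach a better plateau at the same speed. Followed as written, the plan reports whether TENS changes the speed of adaptation, and does not directly report whether it increases the symmetry gained. The one tied-belt period after training, where symmetry following training could be seen, contributes fNIRS data to the models but no gait data.

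Savings is a second difficulty. It compares two visits that always differ in TENS status, so it mixes retention with the immediate effect of TENS.

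If a symmetry measure or a stride window is added later to fill the gap, it will be chosen by an unmasked team that reviews the data monthly (III.N.1).

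**Working it through.** **The plan's own figure.** The only sample-size figure is 10 per group (II.B.3), for an effect size of 1.01 on SMA activity. A two-sided paired t-test at alpha 0.05 gives power 0.756 at n = 9 and 0.811 at n = 10, so the figure reproduces. It concerns brain activity and says nothing about power for any gait outcome.

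**Hypotheses against outcomes.**
- More symmetry gained with TENS (I.A.2): no outcome measures the amount gained; rate is the nearest.
- Better retention with TENS (I.A.2): savings is the named outcome.
- Symmetry change in deadaptation (III.D.2): no modelled gait outcome.

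**Can rate stand in for symmetry gained?** The documents give no SLA values, so everything in this step is assumed. Let SLA at stride k = plateau + (start - plateau) x exp(-k/tau). Let TENS move the plateau from -0.10 to -0.05, with tau = 50 strides in both conditions and a start of -0.40, -0.30 or -0.20.
- Rate as time constant: 50 against 50, difference 0.
- Rate as initial slope, (plateau - start)/tau: ratios 0.35/0.30 = 1.17, 0.25/0.20 = 1.25, 0.15/0.10 = 1.50.
- Rate as strides to reach -0.15, tau x ln[(start - plateau)/(-0.15 - plateau)]: 89.6 to 62.6, 69.3 to 45.8, 34.7 to 20.3, which is 30% to 42% fewer.

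Two of the three definitions register the gain, but they do not identify it. From a start of -0.40, a pure speed effect (plateau -0.10 in both conditions, tau falling from 50 to 35) also takes strides to -0.15 from 90 to 63. Over the last 30 of an assumed 400 strides, mean SLA then differs by about 0.00013, against 0.05 under the plateau effect.

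**What savings compares.** This step is algebra with no assumed values. Let m be the rate at visit 1 without TENS, S the gain from having done visit 1, T the immediate effect of TENS on rate, and R the amount that TENS at visit 1 adds to the visit 2 rate.
- OFF then ON: savings = (m + S + T) - m = S + T.
- ON then OFF: savings = (m + S + R) - (m + T) = S + R - T.
- TENS-first minus TENS-second: R - 2T.
- Crossover TENS estimate on rate, half the difference of the two sequences' visit changes: [(S + T) - (S + R - T)]/2 = T - R/2.

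The sequence difference in savings is therefore -2 times the crossover estimate. With complete data this is an identity, and it also holds with visit x TENS in the model. In a simulated complete data set (n = 30) the savings difference was -1.0519 and the mixed-model TENS estimate 0.5260, with test statistics -2.873 and 2.873. For R = 0, T, 2T and 3T the savings difference is -2T, -T, 0 and +T.

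**Absolute or signed change in deadaptation?** Take a baseline SLA of +0.02 and deadaptation values of -0.05 or -0.10 (assumed). Change in absolute SLA is 0.05 - 0.02 = +0.03 or 0.10 - 0.02 = +0.08. The size of the signed shift is 0.07 or 0.12. The second participant ends further from symmetry: absolute change scores that as worse, while signed change scores it as the larger effect. Only the absolute change measures symmetry gained; the signed change measures after-effect size.

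**The case against.** The strongest reply is that symmetry improvement in I.A.2 is loose wording for adaptation. The stated objective there is adaptability, the Background (I.B.4) predicts better gait adaptability, and III.D.1 says "Our outcome measures assessing gait adaptation will be step length asymmetry (SLA"), from which rate and savings follow. On that reading the outcomes fit and only the sentence is loose. This has force, and it is why rewording the hypothesis is an acceptable remedy. It does not make rate a measure of symmetry gained. The reference to gait kinematics and kinetics in III.N.1 is too general to supply one: it names no outcome, window or model.

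Four stronger readings are tempting, and the documents do not support them.
- That the symmetry hypothesis is untested. Rate is derived from SLA, and some definitions would register a gain.
- That the protocol promised a TENS comparison in deadaptation. III.D.2 speaks of groups and names no ON/OFF contrast; tying that period to the TENS hypothesis is an inference. The earlier work cited in I.B.2 reports gains after training, but its endpoints are not given.
- That savings always makes TENS look bad. It does so only when R is less than 2T.
- That savings is worthless. Comparing it between people with MS (PwMS) and controls is unaffected by the identity.

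Two cautions about using deadaptation also stand. At TENS ON visits, deadaptation begins just as TENS switches off, so very early strides may reflect that change. In participants who start near symmetry, absolute SLA has little room to improve.

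**Conclusion.** The point stands and should be corrected before analysis, with medium confidence. Of the two TENS hypotheses on gait, the one on symmetry gained has at best an indirect test, and the indirectness depends on a rate formula that is not given. Deadaptation SLA is recorded for a stated purpose and modelled nowhere. These findings rest on the text alone.

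The savings result is exact for complete data: compared by sequence, savings restates the TENS effect on rate, doubled and with its sign reversed, and adds no separate evidence on retention. Reading it as poorer retention in the TENS-first sequence would be an error whenever T is positive and R lies between 0 and 2T.

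The size of the gap between rate and symmetry gained is unknown. The range from 0 to 50% rests on assumed SLA values, an exponential curve and an equal time constant. It shows that the two can diverge, not how far they will in this trial.

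**What to change.** In the SAP (V.C):
- Add one main symmetry outcome per participant-visit: change in absolute SLA from that visit's tied-belt baseline to a fixed deadaptation stride window. Fit it in the same mixed model and report the TENS effect and group x TENS. Both periods are tied-belt at preferred speed with TENS OFF. Choose the window with the switch-off at ON visits in mind, and say so.
- Report two supporting outcomes: signed SLA change in the same window, labelled as after-effect size and not symmetry gained, and SLA in a fixed late-adaptation window. For controls, use the fast-belt limb as the sign reference; this matches PwMS, whose fast belt is set for the more affected leg (III.D.2).
- State the formula for adaptation rate.
- State that savings compared by sequence restates the TENS effect on rate and will not be read as a test of TENS on retention. The comparison of savings between PwMS and controls can stay.

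Alternative: reword the hypothesis in I.A.2 to speed of adaptation, drop the claim that savings tests TENS retention, and state how deadaptation SLA will be analysed.

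Cost: wording, and outcomes derived from data already collected. The downside is more tests, since the false discovery rate is controlled within each outcome and not across outcomes. With one TENS test per outcome, no TENS effect and independent outcomes, the chance of at least one false positive is 1 - 0.95^m. That is 5% for rate alone (savings by sequence repeats it), 9.8% with the main symmetry outcome, 14.3% with one supporting outcome and 18.5% with both. It is higher if group x TENS is also counted. Naming one main outcome limits this.

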- **TENS Protocol.** 30 PwMS and 30 age- and sex- matched controls will be randomized into two groups and complete two split-belt treadmill training sessions identical to Aim 1, while outfitted with cortical fNIRS and TENS devices on their bilateral tibialis anterior and rectus femoris. The first group will complete split-belt treadmill training with TENS OFF during the first visit (these are the participants in Aim 1) and TENS ON during the second visit. The second group will complete split-belt treadmill training with TENS ON during the first visit and TENS OFF during the second visit to control for a learning effect. In between visits there will be a 4-week washout period (Figure 3). Participants will receive TENS only during the 10-minute split-belt adaptation period of the paradigm. During all other periods the TENS will be OFF. We will use an FDA-approved clinical TENS device, the LG-TECELITE Therapy System (LGMedSupply, Cherry Hill, NJ). Stimulation will consist of bursting biphasic pulses delivered with electrode pairs (2 in. \times 4 in. pads) placed on the skin over the

INSTITUTIONAL REVIEW BOARD NON-EXEMPT PROTOCOL TEMPLATE

stimulated muscles. The stimulus frequency will be set at 5 Hz with a seven pulses of 0.15 ms based on recent evidence suggesting that bursting TENS is most effective for improving walking performance and limits nerve accommodation to the stimulation. The amplitude of the TENS stimulation will be individualized for each participant in accordance with their specific motor threshold. The TENS amplitude will be slowly increased at 1 mA increments on each individual muscle until non-voluntary muscle contractions can be seen or felt by the investigator, then the amplitude will be set to 2 mA below the motor threshold for each muscle and limb during the split-belt adaptation period. Additionally, we are choosing to outfit TENS on the tibialis anterior and rectus femoris due to previous studies successfully improving gait performance in PwMS using these stimulation locations (Figure 3).

[figure not shown]

Figure 3. (Left) Study design schematic including randomization and TENS condition at each visit. (Right) Example of TENS electrode placement on the bilateral tibialis anterior and rectus femoris.

- **Clinical Assessments**

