- C. Statistical Analysis Plan:** In this crossover design, PwMS and healthy control participants will be pseudo-randomized to begin in either the TENS First or TENS Second condition. Randomization will be performed using a random number generator and will be counterbalanced across age, sex, and fast limb to ensure group balance. A predefined list of participant numbers with corresponding randomized assignments will be generated prior to enrollment. Linear mixed-effects models will be used to identify differences in adaptation and fNIRS outcomes, with group (PwMS vs. healthy controls), visit (Visit 1 vs. Visit 2), and TENS condition (TENS ON vs. TENS OFF), along with their interactions, as fixed effects, and participant number as a random effect. Assumptions of linearity, normality of residuals, and homoscedasticity will be tested for each model. Following model creation, a repeated measures ANOVA will be performed for each adaptation outcome (adaptation rate and adaptation savings) and for cortical activation (HbO beta). Type III ANOVAs with Satterthwaite's method for degrees of freedom estimation will be used for all analyses. Post-hoc comparisons will be conducted using estimated marginal means (EMM) to further investigate significant main effects and interactions. P-values will be corrected using the Benjamini–Hochberg false discovery rate within each outcome and group when applicable. Cohen's d will be calculated to quantify effect sizes. Separate regression models will be conducted to assess the influence of demographic covariates on primary outcome models. All statistical analyses will be conducted using the lme4 and emmeans packages within R and were two-tailed with an alpha threshold set at 0.05.

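### The number of controls to be randomised is 20 in Study Type and Design but 30 in the TENS Protocol, and only 20 agrees with the stated enrolment of 50

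*Combined protocol and SAP*

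**What the plan says.** Section II.A (Study Type and Design) states that "30 PwMS and 20 neurotypical controls be randomized into two groups". Section II.B.2 then gives "Total number of subjects to be enrolled at this site: 50". The line above it, II.B.1, puts a separate count at 60 and labels it "Total number of subjects who will be approached (including screen fails, controls and subject withdrawals".

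Section III.D.2 (TENS Protocol) states that "30 PwMS and 30 age- and sex- matched controls will be randomized into two groups".

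Section II.B.3 contains the only sample-size justification. It uses an effect size of 1.01 for the change in supplementary motor area activity, alpha 0.05 and power 0.8, and concludes that "at least 10 participants per group are needed to detect significant changes in brain activity".

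The Statistical Analysis Plan (V.C) gives no group sizes. It does say that "A predefined list of participant numbers with corresponding randomized assignments will be generated prior to enrollment".

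**The concern.** The two sections describe one study and give two sizes for it. Both set out the same pair of sequences (stimulation off then on, and on then off), the same 4-week washout, the same restriction of stimulation to the 10-minute adaptation period, and the same muscles. The differing control numbers therefore cannot be read as belonging to two separate cohorts. Both sections are current text, so this is not a difference between superseded and current wording.

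The control number fixes the enrolment target, the ratio of controls to people with MS, and the precision of the comparison between them. That comparison is one of the study objectives (I.A.2), and group is a fixed effect in the planned mixed models (V.C). The assignments are to be generated before enrolment starts, so the number should be settled before then.

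**Working it through.** **Inputs.** People with MS: 30 (II.A and III.D.2). Controls: 20 (II.A) or 30 (III.D.2). Enrolled: 50 (II.B.2). Approached: 60 (II.B.1). Effect size 1.01, alpha 0.05, power 0.8, minimum 10 per group (II.B.3). Two-tailed tests (V.C). Payment for completing the study: $100 (III.F).

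**1. Reproduce the stated enrolment.** Enrolled = people with MS + controls.

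| Source | Sum | Against enrolled, 50 | Left over from 60 approached |
|---|---|---|---|
| II.A | 30 + 20 = 50 | equal | 60 − 50 = 10 (10/60 = 16.7%) |
| III.D.2 | 30 + 30 = 60 | 60 − 50 = 10 too many (10/50 = 20%) | 60 − 60 = 0 |

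The figures in II.A reproduce the enrolment line exactly and those in III.D.2 do not. The 60 in II.B.1 does not rescue them, because by its own label it includes people who fail screening or withdraw. With 30 controls, everyone approached would have to enrol.

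**2. Reproduce the stated minimum per group.** The calculation is the power of a two-sided paired t-test from the noncentral t distribution, with n − 1 degrees of freedom, noncentrality 1.01 × √n and alpha 0.05.

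- n = 10: power 0.811. This is the smallest n that reaches 0.8, so the stated minimum reproduces as a within-group calculation.
- n = 20: power 0.990.
- n = 30: power above 0.999.

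The power statement is satisfied with either number of controls, so it cannot decide between them.

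**3. Effect on the group comparison.** As a guide only, take one value per person and equal variances. The standard error of the difference in means is then proportional to √(1/30 + 1/n controls).

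- 20 controls: √(1/30 + 1/20) = 0.289.
- 30 controls: √(1/30 + 1/30) = 0.258.

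The ratio is 0.258/0.289 = 0.894, a standard error about 11% smaller with 30 controls. The planned mixed model uses repeated values per person, so this shows the order of the effect and not the trial's actual precision.

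**4. Cost of the larger number.** 10 extra controls × $100 = $1,000 in participant payments.

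**The case against.** **The repair may be one number, and little depends on it.** The design statement and the enrolment line agree at 50, the analysis model does not depend on the control number, and the stated minimum is met either way. All of that is true, and it limits the consequence. It does not remove the contradiction: the protocol still gives two randomised totals, and only one fits its own enrolment line.

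**A reader might infer that the TENS Protocol is simply the wrong section.** The enrolment line favours 20, but 50 may be no more than the sum 30 + 20, so it is not clearly independent evidence. III.D.2 speaks of matched controls, and III.A.2 relies on matching to deal with age as a confounder. Equal numbers would fit one-to-one matching. Against that, II.A also describes its 20 controls as matched, and no ratio is stated anywhere. The supportable statement is that 30 does not agree with the stated enrolment. Which number is intended remains open.

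**A reader might infer that 20 controls leave no margin on power.** III.D.2 describes one sequence as "TENS OFF during the first visit (these are the participants in Aim 1) and TENS ON during the second visit". If the brain-activation analysis used only that sequence, an equal split would leave 20/2 = 10 controls, exactly the stated minimum. The documents do not support this. They never define Aim 1 by number. II.A equips all randomised participants with fNIRS at both sessions, and V.C models the fNIRS outcomes with visit and stimulation condition as fixed effects, which draws on both sequences. The item directly after the power statement also uses the word groups for diagnosis: "Simple randomization will occur (TENS first or TENS second) for both groups (PwMS and neurotypical controls". II.A does use the same word for the sequences, so the wording alone is not conclusive, but the analysis plan points away from the narrow reading.

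**A reader might infer that a list built from III.D.2 would enrol people beyond the approved number.** V.C gives no list length, and unused entries on a pre-generated list enrol nobody. That harm is not shown.

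**Conclusion.** The point stands as an inconsistency between sections. As written, one of the two control numbers must be wrong. The discrepancy is 10 controls: a total of 50 against 60, or 20% of the stated enrolment. Keeping 30 without other changes would also leave no allowance for screen failure among the 60 approached.

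This conclusion rests only on the documents' own counts and on II.A and III.D.2 describing the same crossover, which their matching design details establish. It makes no claim about which number the sponsor intends, and it is not a finding that the study is underpowered. The consequence lies in the enrolment target and in the size and precision of the comparison between people with MS and controls.

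**What to change.** The sponsor should confirm one control number and use it throughout.

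- **If 20 is intended:** change the 30 controls in III.D.2 to 20. This is one number, with no extra participants.
- **If 30 is intended:** change the controls in II.A to 30 and the enrolled total in II.B.2 to 60, and raise the approached total in II.B.1 above 60 so that it again allows for screen failures. This is three numbers, 10 more controls to recruit and $1,000 in additional participant payments.

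In either case, build the pre-generated assignment list described in V.C to the number kept. It would also help to state the control group size in V.C, which at present gives none.
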